patient should be placed on additional asthma maintenance therapy in the interest of patient safety. Meeting 1 of these criteria does not automatically require a patient to be placed on alternative asthma therapy; rather it requires a clinical evaluation to determine if the patient's asthma can continue to be managed on the current regimen per the study or necessitates a change in asthma maintenance therapy:

- morning FEV₁ by handheld spirometer, as measured at home, falls below the FEV₁ stability limit (FEV₁ <80% of the screening visit FEV₁ measurement that was measured in the clinic during the screening period) for the run-in period and the baseline value (by handheld device) determined at the randomization visit (V3) for the treatment period on 4 or more days out of any 7-day period. These values are based on the handheld device.
- FEV₁, as measured at the study center, is below the FEV₁ stability limit value calculated at the randomization visit (V3) (<80% of baseline by clinic-based spirometry).
- based upon a review of patient diary data, the patient has experienced any of the following during any 7-day period (the days need not be consecutive and may overlap visits):
 - 3 or more days in which 12 or more inhalations/day of rescue medication (albuterol eMDPI or equivalent albuterol/salbutamol) were used
 - 3 or more days with a night-time asthma symptom score of 3 or higher.
- patients who, by the assessment of the investigator, are identified as having experienced a clinically meaningful worsening of their asthma warranting a change in their asthma treatment (based on the investigator's judgment) will start appropriate treatment. A patient may be deemed by the investigator as having a clinically meaningful worsening of their asthma even when they do not meet the alert criteria above.

[figure not shown]
Patients who require a change in background asthma maintenance treatment should complete assessments as outlined for V8 and continue to participate in all laboratory and safety assessments lung function, completion of questionnaires and daily diary assessments. (If a patient requires a change in medication between V8 and V9, the procedures for V9 should be completed. If a change of medication occurs within 2 weeks of the next planned visit, that visit may be skipped). Patients who withdraw consent or are withdrawn from participation in the study should complete the procedures for the Early Withdrawal Visit (EWV).

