6.1.2. Clinical Asthma Exacerbation

For this study, a CAE is defined as worsening asthma requiring treatment with a systemic corticosteroid for ≥ 3 days, emergency room visit resulting in systemic corticosteroid treatment, or hospitalization due to asthma.

Worsening asthma includes new or increased symptoms or signs that either worry the patient, or are related to an asthma-specific alert (if available through the electronic diary/handheld spirometer) and require the addition of maintenance medications (other than systemic corticosteroids) to control the patients asthma symptoms based on the investigator's judgment.

A patient who meets criteria for an asthma exacerbation will be treated per the local standard of care. Additional medication and/or medical intervention that would satisfy the definition of asthma exacerbation occurring within 7 days of the last day of a prior asthma exacerbation event will be considered as part of the same event for analysis purposes.

The asthma exacerbation start and stop dates will be collected in order to determine the exacerbation duration. The start date of an asthma exacerbation will be the start date of the initial medical intervention (ie, use of systemic corticosteroids [oral or injection] asthma-specific hospital admission, or asthma-specific emergency department visit resulting in systemic corticosteroid treatment, whichever comes first). The stop date is the last day of systemic corticosteroids or the last day of an asthma-specific hospitalization whichever is later.

In the event of a CAE, FEV₁ and PEF measurements should be obtained if it is safe to do so in the investigator's opinion. Blood samples to test TEV-53275 serum concentration, ADA, and free and total serum IL-5 levels should be collected if possible.

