9.1. Sample Size and Power Considerations

The sample size is calibrated based on simulation studies to assess the operating characteristics of the following Bayesian success criterion for the final analysis of the primary efficacy endpoint: adjusted mean change from baseline at week 12 in trough FEV₁:

Data from previous internal clinical studies of another anti-IL5 biologic treatment (CinqAir^{®1}) in patients with persistent eosinophilic asthma were used to derive the expected range of treatment effects of TEV-53275 versus placebo and the standard deviation estimate of 0.350 L for the primary efficacy endpoint, when TEV-53275 is given as an add-on maintenance therapy on top of the background ICS or ICS/LABA treatments.

The statistical software FACTS v6.4 was used for conducting the simulations assuming a 15% dropout rate for the placebo group and an 8% dropout rate for each of the TEV-53275 treatment groups.

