Where appropriate, remote assessment of safety via telephone and/or VC, with VC being the preferred method, is recommended until the patient attends his/her next scheduled visit. All other tests (including safety laboratory tests, pharmacokinetics, ADA, and biomarkers) are to be conducted once the patient can return to the study center for his/her next scheduled visit.

Section 4.5 Replacement of Patients

In the event of an emergency situation (eg, COVID-19 outbreaks), if the proportion of patients who terminate the study early due to reasons other than loss of asthma control exceeds the anticipated 15%, the number of patients to be randomized may be increased to ensure the targeted number of completers per arm.

Section 6. Assessment of Efficacy

In the event of an emergency situation (eg, COVID-19 outbreaks), if a patient cannot return to the clinic for the scheduled visits (eg, due to quarantine, isolation, patient's concern, active COVID-19 infection, or closure of the site clinic), remote assessment of efficacy via telephone call and/or VC, with VC being the preferred method, may be allowed. Uploaded electronic diary data for rescue medication usage, daytime and night-time asthma symptom scores, and uploaded hand-held spirometry data will be reviewed remotely. Telephone/VC assessment by the investigator will be assessed at the scheduled visit. Clinic-based forced expiratory volume in 1 second (FEV₁) assessments will not be possible unless a satisfactory home spirometry device that is generally equivalent can be implemented. The results of the clinical asthma exacerbation (CAE) inquiry will be entered directly into the CRF per the usual process. Questionnaire data will be completed and entered into the CRF per the usual process or will be collected by validated paper questionnaire and entered into the database by the study personnel.

Preferably, the original protocol instructions will be followed whenever the new instructions are not required.

These measures will be implemented on a case-by-case basis, and only when and where they are warranted due to the emergency situation. Preferably, the original protocol instructions will be followed whenever the modified instructions are not required.

Section 7. Assessment of Safety

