6.3.8. Time to First Clinical Asthma Exacerbation (CAE) Throughout the Study

The time (days) to the first CAE is the interval from the randomization to the occurrence of the first CAE.

The observation for each patient is the interval from randomization to the occurrence of the first CAE, or censoring, whichever occurs earlier. It is derived as:

the date of censoring or the date CAE - the date of randomization + 1.

Patients who early terminated from the study without CAE due to lack of efficacy or an asthma-related AE will be also treated as experiencing CAE at the time of early withdraw visit.

Patients who complete the week 16 visit without CAE will be right-censored at the time of Week 16 visit. Patients without CAE and early withdrawn from the study before the week 16 with reasons other than lack of efficacy or asthma-related AEs will be right-censored at the time of early withdrawal visit.

The Kaplan-Meier (KM) method will be used to estimate and compare the distributions of time to the first CAE between treatment groups. Distribution difference will be compared by a log rank test adjusting for the randomization stratification factors.

[REDACTED]

6.3.9. Changes From Baseline in Asthma Control Questionnaire (ACQ-6) at Weeks 12 and 16

The ACQ-6 is a validated asthma assessment tool that has been widely used. The 6 questions are self-assessments (completed by the patient). Each item on the ACQ-6 has a possible score ranging from 0 to 6, and the total score is the mean of all responses. ACQ-6 will be administered at visit 2/run-in, visit 3/DoR, visit 5/week 2, visit 6/week 4, visit 7/week 8, visit 8/week 12, and visit 9/week 16 or early withdrawn visit.

The mean total score of the ACQ-6 is derived as the average of the individual item scores. For incomplete data, the following rules will apply:

1. Mean total score for a visit will not be calculated if Question 1 is left blank, irrespective of the completion of the remaining questions.
2. A missing score on post-baseline questionnaire for Questions 2-6 will be imputed based on the total scores from the previous visit, as long as at least 3 out of the 5 questions have responses for the current visit (ie, at least half of the remaining questions are answered).

The formula is: (total sum of non-missing scores for the current visit / total sum of scores for the previous visit for questions answered for the current visit) * (score for the missing question on the previous visit)

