13.1.3. Early Stopping with a Smaller Sample Size

Due to challenges in patient enrollment in the face of COVID-19 pandemic, the feasibility of an early stopping of the trial with smaller sample sizes will also be evaluated during the interim analysis. The unblinded assessment is based on

Posterior probability (TEV-53275 1200 mg treatment effect vs placebo >0 at interim analysis) for the primary efficacy endpoint (12-week endpoint).

The final trial sample size would be reduced to a smaller number according to the following criteria:

1. Reduce to 80 per arm in case of “Very good” efficacy signal:

Posterior probability ≥ 0.95 ;

2. Reduce to 90 per arm in case of “Good” efficacy signal:

$0.95 > \text{Posterior probability} \geq 0.9$;

3. Keep 100 per arm when the efficacy signal is not as good, but not futile:

Posterior probability < 0.9 .

Simulations were conducted to assess the operating characteristics of the early stopping rules. The simulations took into account the non-binding futility stopping specified in Section 13.1.2. When the futility criterion is met, a simulated trial is stopped due to futility with a probability of 50% or 30%. For the purpose of estimating type 1 error rates and study powers using simulations, the posterior distributions for the mean responses were derived using the conjugate priors for the means with a known standard deviation of 0.35 L in the Bayesian analysis. The priors follow normal distributions with mean 0 for all treatment groups. The simulations assumed a 10% dropout rate and 5000 simulations run were used in each scenario.

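### SAP 6.3.8 counts some withdrawals without an exacerbation as exacerbations, so the result named time to first CAE is a composite that the protocol does not define

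*SAP*

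**What the plan says.** Protocol 6.1.2 gives this definition of a CAE: "worsening asthma requiring treatment with a systemic corticosteroid for ≥ 3 days, emergency room visit resulting in systemic corticosteroid treatment, or hospitalization due to asthma". Sections 3.1 and 6.1.2 agree, and neither makes leaving the study a component. Protocol 9.5.4.3 compares time to first CAE by Kaplan-Meier and a stratified log-rank test, with no rule that turns a withdrawal into an event.

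SAP 6.3.8 keeps that test but adds: "Patients who early terminated from the study without CAE due to lack of efficacy or an asthma-related AE will be also treated as experiencing CAE". The event is dated at the early withdrawal visit. Withdrawals for any other reason are censored there, and completers without a CAE are censored at week 16.

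The visible text of SAP Section 15, which lists changes from the protocol's analyses, covers only the imputation method. The SAP introduction says that the SAP aims to agree with the protocol on all secondary endpoints, that it prevails where the two differ, and that differences will be explained in the study report.

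On dropout, Protocol 9.1 assumes "a 15% dropout rate for the placebo group and an 8% dropout rate for each of the TEV-53275 treatment groups". It gives no breakdown by reason.

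**The concern.** The rule applies to patients whom the SAP itself describes as not having had a CAE. The result keeps the name of the protocol endpoint but counts a wider set of events. Protocol 9.5.4.3 also plans a negative binomial analysis of CAE frequency with no such rule, so two results labelled CAE could rest on different events.

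Event status also depends on whether a patient stays and on how the withdrawal is coded. Protocol 3.1 says: "Patients who require a change in background asthma maintenance treatment should complete assessments as outlined for V8 and continue to participate". A patient who worsens, has maintenance therapy added and remains is not an event. A patient with the same course who leaves for lack of efficacy is one. Under Protocol 4.4, a withdrawal may be coded as need for a prohibited medication instead of as an adverse event, and SAP 6.3.8 would then censor it.

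At stake is the reading of a secondary result. If qualifying withdrawals are more frequent on placebo, a reported delay in CAEs could contain no difference in CAEs. Neither document adjusts for multiplicity, so a nominal p-value would stand as reported.

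**Working it through.** **The plan's own figure.** The visible text gives no power or event count for CAE. The only stated power is 80.6%, for FEV₁ (SAP 2.4: effect 0.1 L, SD 0.35 L, one-sided 15%). With 100 per arm less 15% and 8% dropout, 85 and 92 patients remain. Normal power = Φ(0.1/[0.35·√(1/85+1/92)] − 1.036) = Φ(1.899 − 1.036) = 80.6%. This fits, but 85/85 (79.6%) and 90/90 (81.1%) come close. It is consistent with the unequal dropout being built into the plan and does not prove it.

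**Inputs from the documents.** 100 per arm (300 randomized 1:1:1), 112 days, dropout 15% and 8%, log-rank test at two-sided 0.05 (Protocol 9.5.4).

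**Assumptions, because the documents are silent.** The 16-week CAE risk p is 5%, 10% or 20% and the same in both arms. A share f of dropouts, also the same in both arms, is for lack of efficacy or an asthma-related AE. Event times are exponential, and the test is unstratified.

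**Formulas.** Cumulative hazards over 16 weeks: h_C = −ln(1−p), h_P = −ln(0.85) = 0.1625, h_A = −ln(0.92) = 0.0834.

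- Hazard ratio under SAP 6.3.8 = (h_C + f·h_A)/(h_C + f·h_P).
- Expected events per 100 in an arm with dropout d and hazard h_D = 100·(h_C + f·h_D)/(h_C + h_D)·[1 − (1−p)(1−d)].

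**Example, p = 10% and f = 0.5.** h_C = 0.1054. Hazard ratio = (0.1054 + 0.0417)/(0.1054 + 0.0813) = 0.79. Expected events are 16.4 on placebo and 13.4 on active, of which protocol-defined CAEs are 9.2 and 9.6. The rule therefore adds about 7.2 and 3.8.

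| CAE risk | f | Hazard ratio | Events per 100, placebo : active | Chance of significant benefit |
|---|---|---|---|---|
| 10% | 0 | 1.00 | 9.2 : 9.6 | about 2.5% |
| 10% | 0.25 | 0.86 | 12.8 : 11.5 | 5% to 6% |
| 10% | 0.5 | 0.79 | 16.4 : 13.4 | 9% to 10% |
| 10% | 1 | 0.70 | 23.5 : 17.2 | 20% |
| 5% | 0.5 | 0.70 | 11.9 : 8.7 | 12% |
| 20% | 0.5 | 0.87 | 25.3 : 22.8 | 7% |

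The last column comes from simulation with at least 10,000 trials per row and counts only results favouring active drug (nominal 2.5%).

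**Two controls.** With equal 10% dropout and every dropout counted as an event (p = 10%), the chance is 2.5% to 2.6%. With protocol-defined CAEs only and 15% versus 8% dropout, it is 2.1% to 2.7%.

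**The case against.** The strongest reply is that the documents do not show qualifying withdrawals to be common. Protocol 9.1 gives no reasons for dropout. Appendix N sets its trigger by whether the proportion of "patients who terminate the study early due to reasons other than loss of asthma control exceeds the anticipated 15" percent; SAP 6.3.8 would censor withdrawals of that kind. SAP 13.1.3 says "The simulations assumed a 10% dropout rate", with no split by arm. Patients whose therapy changes are asked to stay, Protocol 4.4 does not name lack of efficacy as a withdrawal criterion, and Protocol 7.1.1 keeps asthma worsening out of adverse events unless serious. All of this argues against a large share, and it stands.

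A reader might infer that the added events fall mainly on placebo. That needs the whole 7-point excess to be efficacy-related and no qualifying withdrawals on active drug. Under that extreme, the chance of a significant benefit is about 28% at a 10% CAE risk and 42% at 5%. Nothing in the documents supports the premise, so these figures are not a fair measure of size.

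The rule also has a purpose: censoring patients who leave because treatment failed may be informative. Which analysis should lead is partly a trade-off. A difference in such withdrawals would be a real drug effect, though on the composite and not on CAEs.

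Finally, text after the log-rank sentence in 6.3.8 is blacked out, so a strict-definition run may already exist and cannot be called missing. None of this removes the mismatch between the endpoint's name and the events counted.

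**Conclusion.** The mismatch is established from the text alone. What SAP 6.3.8 would report as time to first CAE is time to first CAE or treatment-failure withdrawal, and the visible Section 15 does not record the change.

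The effect on the result is conditional. It needs unequal dropout and some efficacy-related share. At a 50% share in both arms, the chance of a nominally significant benefit with equal CAE risk runs from about 12% to 7% as the assumed CAE risk goes from 5% to 20%. A reader might conclude that the rule manufactures a benefit from nothing. The documents do not support that: with no qualifying share or equal dropout the error rate stays nominal, and where it rises, the arms do differ in withdrawals.

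Severity is minor to moderate. This is one of twelve secondary efficacy endpoints, and it has no visible role in the success criterion, which rests on FEV₁.

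**What to change.** In SAP 6.3.8:

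- Report time to first CAE as defined in Protocol 6.1.2 under the CAE name, censoring patients who withdraw without a CAE at their last contact.
- Report the current rule as a separate analysis labelled *CAE or withdrawal for lack of efficacy/asthma-related AE*.
- State for each arm how many events that rule adds.
- List the change in SAP Section 15.

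If the blacked-out text already holds a strict-definition run, only the labels, the added-event counts and the Section 15 entry are needed.

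The cost is SAP wording and one further Kaplan-Meier and log-rank run. The strict analysis will have fewer events, and its censoring may be informative; the composite analysis beside it addresses that.

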The Standardized Asthma Quality of Life Questionnaire AQLQ[S]) will be self-administered by patients. The questionnaire is a tool to measure the impact of asthma on a patient's quality of life (physical, emotional, social, and occupational). The questionnaire contains 32 items with a 2-week recall period and uses a 7-point Likert scale (7=not impairment at all to 1=severely impairment). Scores range from 1 to 7, with higher scores indicating better quality of life. The 32 questions (items) in the AQLQ(S) are divided in to 4 domains and the corresponding questions are:

- Symptoms: 6, 8, 10, 12, 14, 16, 18, 20, 22, 24, 29, 30
- Activity Limitation: 1, 2, 3, 4, 5, 11, 19, 25, 28, 31, 32
- Emotional Function: 7, 13, 15, 21, 27
- Environmental Stimuli: 9, 17, 23, 26

AQLQ(S) will be measured at visit 3/DoR, visit 8/week 12, and visit 9/week 16 or early withdrawn visit.

The overall and domain mean scores of the AQLQ will be derived as the average of the corresponding items. For incomplete data, the overall mean score for a particular visit will not be calculated if 3 or more responses are missing with no more than 1 per domain. For the symptom and activity domain mean scores, calculation will require no more than 1 missing item. The mean domain score for the other 2 domains will be regarded as missing if 1 or more item is missing.

The changes from baseline in AQLQ(S) at week 12 and week 16 will be analyzed, respectively, using ANCOVA in a manner analogous to the analysis as described Section 6.3.4. The analyses will be for the overall mean score and mean score of each domain. The baseline in the model will be baseline overall mean score of AQLQ(S) or baseline mean score of AQLQ(S) for the domain, respectively.

6.3.12. Proportions of Patients Who Achieve FEV₁:FVC (Forced Vital Capacity) Ratio ≥ 0.80 at Weeks 12, 16, And at Endpoint

The proportions of patients who achieve FEV₁: FVC ratio $\geq 80\%$ will be analyzed using the repeated measures logistic regression model in a manner analogous to the analysis as described Section 6.3.1. Baseline FEV₁: FVC ratio will be used in the model. The analysis will be applied those with baseline FEV₁: FVC ratio < 0.80 .

The analysis will include data up to visit 9/week 16.

6.4. [REDACTED]

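### SAP 6.3.11 places the one-per-domain limit inside the condition for withholding the overall AQLQ(S) score, so read literally a score is still computed from badly incomplete forms

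*SAP*

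**What the plan says.** Change from baseline in AQLQ(S) at weeks 12 and 16 is listed among the secondary efficacy endpoints (SAP 1.1). SAP 6.3.11 describes the instrument ("The questionnaire contains 32 items with a 2-week recall period"), assigns every item to one of four domains, and forms the overall and domain scores as item averages.

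For incomplete forms, the overall mean score at a visit "will not be calculated if 3 or more responses are missing with no more than 1 per domain". The domain rules come next. Symptom and activity scores tolerate a single missing item. For the rest, "The mean domain score for the other 2 domains will be regarded as missing if 1 or more item is missing".

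The protocol's description of the instrument (section 6.1.8) has no missing-item rule. Protocol 9.3.1 leaves detailed imputation rules to the SAP, and the SAP's introduction says the SAP governs where the two differ. The sentence in SAP 6.3.11 is therefore the only rule available for the overall score.

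**The concern.** A limit of one missing item per domain makes sense as a requirement for calculating a score. In this sentence it is attached to the requirement for not calculating one. Withholding then needs two things at once: at least 3 items missing, and those items spread thinly. Concentrated gaps fail the second test and so escape withholding.

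The rule decides who enters the analysis. AQLQ(S) is collected only at visit 3, week 12, week 16 or early withdrawal. SAP 6.3.11 analyses it by ANCOVA with the baseline score as covariate, and SAP 4.3 uses observed data only unless stated otherwise. A score computed from a fragment of the form would enter as an outcome or a covariate with the same standing as a complete one. A programmer would have to code a rule that nobody is likely to want, or guess at the intended one, and the second defeats prespecification.

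**Working it through.** **Inputs, all from SAP 6.3.11.** The domains are:
- "Symptoms: 6, 8, 10, 12, 14, 16, 18, 20, 22, 24, 29, 30", which is 12 items
- "Activity Limitation: 1, 2, 3, 4, 5, 11, 19, 25, 28, 31, 32", which is 11 items
- "Emotional Function: 7, 13, 15, 21, 27", which is 5 items
- the environmental domain, with items 9, 17, 23 and 26, which is 4 items

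**Reproducing the stated figure.** 12 + 11 + 5 + 4 = 32, and each item from 1 to 32 appears exactly once. This agrees with the stated 32 items.

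**The literal condition.** Let m be the total missing and d the largest number missing in any one domain. The score is withheld if m ≥ 3 and d ≤ 1. With four domains, d ≤ 1 forces m ≤ 4, so only m = 3 or m = 4 can meet both parts. If m ≥ 5, some domain must have at least 2 missing, the second part fails, and nothing is withheld.

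**Counting patterns.**
- m = 3: all patterns, C(32,3) = 4,960. Patterns in three different domains: 12×11×5 + 12×11×4 + 12×5×4 + 11×5×4 = 660 + 528 + 240 + 220 = 1,648. Withheld: 1,648 / 4,960 = 33.2%.
- m = 4: all patterns, C(32,4) = 35,960. One per domain: 12×11×5×4 = 2,640. Withheld: 2,640 / 35,960 = 7.3%.
- m ≥ 5: withheld 0.

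These are shares of possible patterns, not of patients. They show that the literal rule becomes more lenient as more items go missing.

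**Specific forms.** The last two columns are candidate restatements, shown as assumptions. Each requires at most one missing item per domain; they differ only in the limit on the total.

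| Missing items | Answered | Literal sentence | Fewer than 3 in total | At most 3 in total |
|---|---|---|---|---|
| 2, different domains | 30 | calculated | calculated | calculated |
| 2, same domain | 30 | calculated | withheld | withheld |
| 3, three domains | 29 | withheld | withheld | calculated |
| 3, same domain | 29 | calculated | withheld | withheld |
| 4, one per domain | 28 | withheld | withheld | withheld |
| All environmental | 28 | calculated | withheld | withheld |
| All emotional | 27 | calculated | withheld | withheld |
| All activity | 21 | calculated | withheld | withheld |
| All symptom | 20 | calculated | withheld | withheld |
| 31 items | 1 | calculated | withheld | withheld |

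Both restatements withhold every form with a whole domain missing. They part only on 3 missing in three domains, the 1,648 patterns counted above.

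**What a missing domain does to the score.** Write S for the symptom-item mean and R for the mean of the other 20 items. The full score is (12/32)S + (20/32)R = 0.375S + 0.625R. With no symptom items, the available-item average is R. The difference is R − (0.375S + 0.625R) = 0.375(R − S), so 37.5% of any gap between symptom items and the rest passes into the score.

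**Against the neighbouring rules.** With all environmental items blank, that domain score is set to missing, yet the overall score is still computed from the other 28. The other questionnaires show no such pattern: for ACQ-6 (SAP 6.3.9) and ACT (SAP 6.3.10), more missing items never turn a withheld score into a calculated one.

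**The case against.** The strongest reply is that the intent is easy to see. The opening part, withholding at 3 or more missing, points the right way, and the neighbouring domain rules suggest that one per domain was meant as a tolerance. A sensible programmer might code it so. That is a fair account of the likely intent, but it concedes that the sentence does not say it.

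A second reply is that the sentence gives one condition for withholding and does not state that every other form is scored. Computing a score from 20 items thus rests partly on silence. This stands as a caution, but no other rule for the overall score is given, and the default is to use observed data. Calculation is the natural reading of the text.

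A reader might also infer something stronger: that the whole rule is reversed, and that withholding a form with 29 of 32 items answered, three missing in three domains, is itself a mistake. The documents do not support this. A plain limit of fewer than 3 missing, which is what the SAP's own cut-off implies, withholds that form too. A limit of at most 3 would keep it. Neither document says which was meant, and no scoring manual is included. Only the placement of the per-domain qualifier is shown to be wrong.

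Finally, the practical effect may be small. The domain-score analyses are protected by their own rules, and only incomplete forms are touched. This also stands, and it sets the weight of the point.

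**Conclusion.** The rule is wrong as written, because the per-domain qualifier sits in the wrong condition. Taken literally it withholds only forms with 3 or 4 items missing, one per domain, and lets through much less complete ones, against the logic of the domain rules beside it. This conclusion assumes that both parts of the sentence govern withholding and that a form not meeting them is scored from its available items.

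The point is minor. It reaches the overall AQLQ(S) score at weeks 12 and 16, and its baseline covariate, for incomplete questionnaires only. How many there will be cannot be derived from the documents. Protocol Appendix N allows paper questionnaires during COVID-19 outbreaks, so some are foreseeable. The week 12 FEV₁ analysis, the sample size and the stated interim criteria, which use FEV₁, do not depend on it.

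**What to change.** Before unblinding, replace the sentence in SAP 6.3.11 with a condition for calculating, for example: the overall score is calculated only if the total number of missing items is below the stated limit and no domain has more than one missing item; otherwise it is set to missing. If the existing cut-off is kept, the limit is fewer than 3 missing in total.

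The sponsor should confirm two consequences when rewriting:
- whether a form with exactly 3 missing, one in each of three domains, is to be kept or withheld
- that a form with 2 missing in one domain, which the literal sentence scores, will now be withheld: C(12,2) + C(11,2) + C(5,2) + C(4,2) = 66 + 55 + 10 + 6 = 137 of the C(32,2) = 496 two-item patterns

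The cost is one SAP sentence and the matching line of the derivation program. No data collection, sample size or other analysis changes.
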